A Multi-Center, Double-Blind, Randomized, Vehicle-Controlled, Parallel-Group Study Comparing Tazarotene Cream 0.1% to TAZORAC® (tazarotene) Cream 0.1% and Both Active Treatments to a Vehicle Control in the Treatment of Acne Vulgaris

	
Investigator’s Global Assessment (IGA) of acne severity Grade 2, 3 or 4
Study Design	A multi-center, double-blind, randomized, vehicle-controlled, parallel-group bioequivalence study with clinical endpoints comparing Tazarotene Cream 0.1% to TAZORAC® (tazarotene) Cream, 0.1% and both active treatments to a vehicle control in the treatment of acne vulgaris.
Investigative Sites	Approximately 25 sites in the United States
Study Conduct	
Eligible subjects will be randomized in a 2:2:1 ratio to one of the three treatment groups (Test, Reference or Placebo) at Visit 1. IP will be dispensed at Visit 1. Subjects will be instructed to apply the first dose on the evening of Day 1 and then continue to apply a thin layer once daily, in the evening, to the affected areas on the face until the evening before End of Study, Visit 4 (Day 85 ± 4 days).
 
Subjects will attend the following scheduled clinic visits:
 
Visit 1 - Screening/Baseline: Day -14 to 1Visit 2 - Interim Visit: Day 28 ± 4 daysVisit 3 - Interim Visit: Day 56 ± 4 daysVisit 4 - End of Study/Early Termination: Day 85 ± 4 days 
Efficacy evaluations will be based on dermatological assessments performed in the clinic. The co-primary endpoints, percent change from Baseline in the inflammatory (papules and pustules) and non-inflammatory (open and closed comedones) lesion counts, are to be evaluated at the Week 12 visit (Day 85 ± 4, End of Study).

Inclusion Criteria	
Healthy male or non-pregnant, non-lactating female, ≥ 12 and ≤ 40 years of age with a clinical diagnosis of acne vulgaris.Females of childbearing potential must not be lactating or pregnant at Visit 1 (as confirmed by a negative urine pregnancy test with a sensitivity of less than 50 mIU/mL or equivalent units of human chorionic gonadotropin) and 

CONFIDENTIAL PROTOCOL

A Multi-Center, Double-Blind, Randomized, Vehicle-Controlled, Parallel-Group Study Comparing Tazarotene Cream 0.1% to TAZORAC® (tazarotene) Cream 0.1% and Both Active Treatments to a Vehicle Control in the Treatment of Acne Vulgaris

	Childbearing Potential Defined as:	Non-Childbearing Potential Defined as:

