10.3.5 Early Termination

If a subject terminates from the study early, all efforts will be made to complete Visit 4 study procedures, obtain any outstanding data and collect all IP. In case of early termination, the Investigator shall fully document the reason for early termination and the date of removal.

In the event that a subject discontinues from the study at any time due to an AE, the reason for discontinuation, the nature of the event and its clinical course must be fully documented. For such a subject, the Investigator should follow the subject until the AE has resolved, has become clinically insignificant, is stabilized, is confirmed to be ongoing at the end of the study or the subject is lost to follow-up. Should a serious adverse event (SAE) be noted, procedures stated in section 10.7.4 must be followed. Should pregnancy be noted, procedures stated in section 10.7.6 must be followed.

Subjects who discontinue early because of lack of treatment effect after completing four weeks of treatment will be included in the Per-Protocol (PP) population as treatment failures provided they had no significant protocol deviations (PDs). Any PD that would compromise the integrity of the data will be considered significant.

Subjects who discontinue early due to a worsening condition and require alternate or supplemental therapy for the treatment of acne during the study should be discontinued, included in the PP population analysis as treatment failures (provided they had no significant PDs during their time of study participation), and referred for effective treatment outside of the study.

Subjects who discontinue early for reasons besides lack of treatment effect or worsening of condition should be excluded from the PP population, but included in the modified Intent-to-Treat (mITT) population using the last observation carried forward (LOCF), provided they administered at least one dose of randomized IP and completed at least one post-dose evaluation.

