10.6.8 Lesion Counts

At each visit the number of inflammatory lesions (i.e., papules and pustules), non-inflammatory lesions (i.e., open and closed comedones) and nodulocystic lesions (i.e., nodules and cysts) on the facial area, including the nose, will be counted and recorded. Counts of each lesion type (i.e., inflammatory, non-inflammatory and nodulocystic) should be reported separately in the source and electronic case report form (eCRF). Definitions of these terms are listed in Appendix C.

Lesion counts should only be conducted by those individuals who have successfully completed the lesion count validation. Wherever possible, the same individual should attempt to perform all lesion counts at all visits for an individual subject.

At Visit 4 (or Early Termination), the lesion counts for the inflammatory and the non-inflammatory lesions will be used to evaluate the primary endpoints of percent change in inflammatory lesion counts and percent change in non-inflammatory lesion counts.

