11.3 Study Populations

11.3.1 PP Population

The PP population will include subjects that comply with the protocol as follows:

- All randomized subjects who meet all inclusion and exclusion criteria.
- Make the final study visit (Visit 4) within the protocol window of Day 85 ± 4 days with no PDs that would affect the integrity of the data.
- Comply with study restrictions including concomitant medications.
- Apply the IP appropriately and are within [REDACTED] compliant with dosing during the 12 weeks (Day 85 ± 4) of treatment.
- Do not miss the scheduled applications for more than [REDACTED]

[REDACTED]

[REDACTED]

[REDACTED]

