11.5 Efficacy Endpoints

Primary Efficacy Endpoints

The two co-primary efficacy endpoints are (1) the percent change from Baseline to Week 12 in the inflammatory (papules/pustules) lesion counts and (2) the percent change from Baseline to Week 12 in the non-inflammatory (open and closed comedones) lesion counts.

Secondary Efficacy Endpoint

The secondary efficacy endpoint is the proportion of subjects who are considered a Clinical Success at Week 12, as defined by an IGA score that is at least 2 grades less than the Baseline assessment. That is, at Week 12, subjects with an IGA score of 4 at Baseline must achieve a score of 0, 1 or 2, subjects

CONFIDENTIAL PROTOCOL

A Multi-Center, Double-Blind, Randomized, Vehicle-Controlled, Parallel-Group Study Comparing Tazarotene Cream 0.1% to TAZORAC® (tazarotene) Cream 0.1% and Both Active Treatments to a Vehicle Control in the Treatment of Acne Vulgaris

with an IGA score of 3 at Baseline must achieve a score of 0 or 1, and subjects with an IGA score of 2 at Baseline must achieve a score of 0 to be considered a Clinical Success.

A Clinical Failure is defined as an IGA score at Week 12 that is the same, higher or one grade lower than the Baseline IGA. Subjects who are discontinued due to lack of treatment effect or worsening condition will be considered Clinical Failures.

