12.3.4 Source Documents and Case Report Forms

All subjects will be identified by initials and date of birth. Randomized subjects will also have a unique subject randomization number. Source documents will be used to record all study-related data. Source document entries will be used to complete eCRF, which will record all critical study information. A set of eCRFs will be completed for each subject enrolled in the study. All data from eCRFs will be reviewed, evaluated and signed by the Investigator, as required. All eCRFs will be cross referenced to source documentation by the study monitor and/or the sponsor to ensure accurate transcription of the data.

The original source documents and a copy of the corresponding eCRFs (electronic or print out) will be retained by the Investigator. Subjects who terminate early from the study will have the Visit 4 (End of Study/Early Termination) Source/eCRF completed.

Primary Source Documents

The Investigator must maintain source documents supporting significant data for each screened subject's medical notes. Standardized source document forms will be utilized for this study and will include original records.

During monitoring visits the monitor will validate data in the eCRFs against the sources of data.

If a subject does not qualify for enrollment, they will be considered a screen failure. The reason for their disqualification will be included in their source document and summarized in the CSR.

Case Report Forms

Source document entries will be used to complete eCRFs for enrolled subjects. All data and eCRFs will be reviewed, evaluated and signed by the Investigator, as required. Further details will be provided in the data management plan.

Supporting Documentation

The Investigator site file will be maintained by the Investigator and study staff and will be available for review during monitoring, auditing and regulatory agency inspections, if applicable.

Details will be provided in the monitoring plan.

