8.2 Efficacy Analyses

8.2.1 Primary Efficacy Analysis

Therapeutic Bioequivalence Analysis

The primary measure of therapeutic equivalence will be evaluated using the PP population, with results in the mITT population being supportive.

The following Statistical Analysis Method is recommended by OGD for equivalence testing for a continuous variable:

The compound hypothesis to be tested is:

$$H_0: \mu_T/\mu_R < \theta_1 \text{ or } \mu_T/\mu_R > \theta_2 \quad \text{versus}$$

STATISTICAL ANALYSIS PLAN

Tazarotene Cream 0.1%

Protocol / 0454-01-01/

$$H_A: \theta_1 \leq \mu_T / \mu_R \leq \theta_2$$

where μ_T = mean percent change from baseline of test treatment, and
 μ_R = mean percent change from baseline of reference treatment

Under the assumptions of normally distributed data, the adjusted 90% confidence interval will be calculated for the Test/Reference ratio of the mean percent change from Baseline in inflammatory and non-inflammatory lesion counts using an iterative procedure similar to Fieller's method. ANOVA with treatment and site as fixed effects in the model will be conducted on the mean percent change from Baseline to Week 12 in the inflammatory (papules/pustules) lesion counts and non-inflammatory (open and closed comedones) lesion counts. If the adjusted 90% confidence intervals for the least-squares mean Test/Reference ratios are within 80-125% for both co-primary endpoints, then therapeutic equivalence of the Test to Reference product will be considered to have been demonstrated.

To declare therapeutic equivalence of the Test product to the Reference product, therapeutic equivalence must be demonstrated for only the primary endpoints in the PP population.

Superiority to Placebo Analysis

The primary measure of superiority will be evaluated using the mITT population, using LOCF for missing efficacy values. The results in the PP population will be considered supportive.

The superiority of the Test and Reference products over Placebo is concluded if these treatments' mean percent changes from Baseline in inflamed and non-inflamed lesion counts at Week 12 are statistically superior to that of the Placebo at the 5% significance level ($p < 0.05$, two-sided). The superiority of Test and Reference treatments over the Placebo will be evaluated in the same ANOVA model for Test vs. Placebo and Reference vs. Placebo.

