8.5 Methods for Handling Missing Data

For demographic and baseline characteristics, each variable will be analyzed using all available

[REDACTED]

STATISTICAL ANALYSIS PLAN

Tazarotene Cream 0.1%

Protocol / [REDACTED] 0454-01-01/[REDACTED]

data. Subjects with missing data will be excluded only from analyses for which data are not available, including denominators.

Subjects discontinued early for reasons other than lack of treatment effect or worsening condition will be excluded from the PP population and included in the mITT population using Last Observation Carried Forward (LOCF), provided they administered at least one dose of randomized IP and completed at least one post-dose evaluation..

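### Do subjects who stop for lack of effect or worsening drop out of the per-protocol equivalence analysis, or enter it without a defined lesion count?

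*Protocol*

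**What the plan says.** **Membership.** Protocol 10.3.5 places two groups of early leavers in PP as treatment failures: those who stop for lack of effect after four weeks ("lack of treatment effect after completing four weeks of treatment will be included in the Per-Protocol (PP) population as treatment failures"), and those who worsen and need other acne therapy. Both must be free of significant deviations. The PP criteria in Protocol 11.3.1, repeated in SAP 6, include "Make the final study visit (Visit 4) within the protocol window of Day 85 ± 4 days". No exception is visible, but redacted lines follow the criteria in both documents. SAP 8.5 says: "Subjects discontinued early for reasons other than lack of treatment effect or worsening condition will be excluded from the PP population".

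**Value.** Protocol 10.6.8 says: "At Visit 4 (or Early Termination), the lesion counts for the inflammatory and the non-inflammatory lesions will be used to evaluate the primary endpoints". Protocol 12.3.4 adds: "Subjects who terminate early from the study will have the Visit 4 (End of Study/Early Termination) Source/eCRF completed". The synopsis ties the co-primary endpoints to the Week 12 visit, and the PP summary shell T16.1.9.7.1 has a Week 12 row only. Listing L16.2.6.1 shows percent change at a combined 4/ET visit.

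**Missing data.** SAP 8.2.1 says: "The primary measure of superiority will be evaluated using the mITT population, using LOCF for missing efficacy values". For the PP equivalence analysis it gives no corresponding sentence.

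**The concern.** Equivalence is declared on the two co-primary endpoints in PP alone; the mITT result is supportive. A subject who leaves at Day 40 for lack of effect satisfies 10.3.5 but not the visit-window criterion. A programmer who works from SAP 6 only could filter that subject out.

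The word failure does not help with the lesion endpoints. It has a defined value only for the IGA outcome (Protocol 11.5: "Subjects who are discontinued due to lack of treatment effect or worsening condition will be considered Clinical Failures"), whereas the ANOVA needs a percent change in lesion count. The LOCF sentence is attached to mITT superiority, and SAP 8.5 assigns LOCF only to those who left for other reasons. On the SAP's wording alone, the PP failures fall between the two rules.

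If Test had more such failures than Reference and they were left out, the Test/Reference ratio would move toward 1, in favour of declaring equivalence.

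**Working it through.** **1. Are these subjects in PP?** Three texts say yes.
- Protocol 10.3.5 names them, and as the specific rule it qualifies the general window criterion.
- SAP 8.5 limits its PP exclusion to those who left for other reasons, so it leaves these subjects in.
- Protocol 10.4.6 judges dosing compliance of early terminators over their own time in the study. That adapts one PP criterion to subjects who leave early.

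The redacted lines after the PP criteria may state the exemption outright, so it cannot be called absent.

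**2. Which lesion count?** Protocol 10.6.8 names the Visit 4 or Early Termination count for the primary endpoints. The schedules in both documents treat Visit 4 as the end-of-study or early-termination visit, and L16.2.6.1 computes percent change at 4/ET. The Week 12 label does not point the other way: the mITT shell T16.1.9.7.2 has the same single row, although mITT includes early leavers through LOCF.

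**3. What if the termination visit is missed?** No visible rule covers this. Lack-of-effect leavers must have completed four weeks, and Visit 2 with its lesion counts falls at Day 28 ± 4, so a post-baseline count will usually exist. Protocol 11.3.2 makes PP a subset of mITT, so the same subjects already need a value for the mITT superiority analysis, where LOCF applies. Using that value in PP is the obvious choice.

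**4. Size.** There is no plan figure to reproduce. The split adds up (444 + 444 + 222 = 1110), but means, SDs, true ratio and PP numbers are redacted. Every input below is assumed.

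*Fieller 90% limits*, without the site term: the roots θ of (mR² − z²vR)θ² − 2·mT·mR·θ + (mT² − z²vT) = 0, with z = 1.645. Take 350 PP subjects per active arm, Reference completers improving 50%, SD 35, completer ratio 0.90, and failures 4% (Test) v 1% (Reference).
- Failures left out: mT = 45, mR = 50, vT = 35²/336 = 3.646, vR = 35²/346.5 = 3.535. Ratio 0.900 (0.819 to 0.988): pass.
- Failures in, with an observed 10% reduction (SD 40): mT = 0.96×45 + 0.04×10 = 43.6; mR = 0.99×50 + 0.01×10 = 49.6. Ratio 0.879 (0.798 to 0.967): fail.
- Failures in at zero change: 0.873 (0.793 to 0.960): fail.

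Over the grid tried (completer mean 45 to 50, SD 35 to 45, completer ratio 0.90 to 1.00), failures of 2% v 2% moved the ratio by at most 0.001 and the lower limit by at most about 0.006. Failures of 4% v 1% or 6% v 2% moved the ratio by about 0.02 to 0.06. At a completer ratio of 1.00 every handling passed.

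*False-pass rate if failures are dropped.* Assume Reference completers improve 55%, failures 5%, SD 33, 340 PP per arm, Reference failures 2%, and a true PP ratio of exactly 0.80. Then muR = 0.98×55 + 0.02×5 = 54.0 and the PP Test mean is 0.80×54.0 = 43.2. With Test failure share f, the Test completer mean is (43.2 − 5f)/(1 − f). The pass probability is 1 − Φ(1.645 − (Test completer mean − 0.8×55)/SE).

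At f = 8%: (43.2 − 0.4)/0.92 = 46.52; 46.52 − 44 = 2.52; SE = 33×√(1/312.8 + 0.64/333.2) = 2.36; 1 − Φ(0.577) = 28.2%.

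| Test v Reference failures | One endpoint | Both endpoints, independent (square) |
|---|---|---|
| 2% v 2% | 4.9% | 0.2% |
| 4% v 2% | 9.6% | 0.9% |
| 6% v 2% | 17.2% | 3.0% |
| 8% v 2% | 28.2% | 8.0% |

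With failures kept, as 10.3.5 requires, the one-endpoint rate is about 5%.

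**The case for a change.** The best case for a change is that Protocol 11.1 gives the missing-data procedure to the SAP, and the SAP does not finish the job. Protocol 10.3.5 settles who is in PP but not the value. Protocol 10.6.8 is a procedures section that the SAP never cites, and completing the termination visit is promised only as a best effort. The decision rests on PP alone, the calculations show that handling can turn a borderline result, and a few sentences written while blinded would remove the choice at almost no cost.

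Part of this stands. No visible SAP sentence carries 10.6.8 into the PP model, no visible rule covers a failure without a termination count, and SAP 8.5 does not repeat the four-week condition. A cross-reference would be tidy.

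The damaging step does not stand. It needs an analyst to drop subjects whom the protocol names as included and whom SAP 8.5 spares. The SAP is written from that protocol and sends its reader to it. The false-pass rates also need a true ratio at the 0.80 limit and Test failing two to four times as often as Reference; nothing in the documents suggests such an imbalance. The one-endpoint rates further suppose that the other co-primary passes easily. Any imbalance would be visible, because T16.1.9.1 tabulates termination reasons by arm and L16.2.1 lists reason and population by subject.

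**Conclusion.** No change is needed. Followed as written, the plan keeps these subjects in PP and gives them their Early Termination count, which is a sound analysis. What is left is detail that an analyst would fill sensibly: a cross-reference in the SAP, and the last post-baseline count when no termination visit took place.

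On the illustrative inputs the effect is negligible when failure shares are equal. It matters only when shares are unequal, the result is borderline, and the subjects are dropped against 10.3.5. This conclusion rests on reading 10.3.5 as a specific exception to the visit-window criterion, and on the redacted lines not saying the opposite. The number of such subjects and their balance between arms are not given, so none of the illustrative rates should be taken as a property of this trial.

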10.4 Treatments

10.4.1 Treatments Administration

At Visit 1, eligible subjects will receive [REDACTED] of randomized IP (Test, Reference or Placebo).

At Visit 2 and/or Visit 3, subjects who continue to be eligible for continuation in the study can be dispensed a [REDACTED] [REDACTED] of IP, as needed, based on the amount of IP remaining from the tube previously dispensed. Further, any empty tubes will be collected at these visits. At Visit 4, all tubes will be collected (used and unused). A subject may return for an Unscheduled Visit at any time, should they require a resupply of IP (i.e., tube lost; all IP used between visits; tube significantly damaged [became punctured]).

CONFIDENTIAL PROTOCOL

A Multi-Center, Double-Blind, Randomized, Vehicle-Controlled, Parallel-Group Study Comparing Tazarotene Cream 0.1% to TAZORAC[®] (tazarotene) Cream 0.1% and Both Active Treatments to a Vehicle Control in the Treatment of Acne Vulgaris

The subject will be instructed on when to apply their first dose of IP, which will be considered Day 1. Females of childbearing potential must administer their first dose (Day 1) during their menstrual period. [REDACTED]

Subjects will be instructed to gently wash the face with the provided mild non-medicated cleanser (e.g., Dove[®] Sensitive Skin or similar), pat dry and then apply a thin layer (2 mg/cm²) of the product to the affected areas of the face, avoiding contact with the eyes, eyelids and mouth.

Subjects will be instructed to apply the IP once daily, in the evening and to wash hands thoroughly before and after each application. The first dose will be applied on the evening of Day 1. Subjects will then continue to apply a thin layer (2 mg/cm²) of the IP once daily, in the evening, through the evening before their final visit for a total of 84 days ± 4 days. There will be no application of the product on the day of the End of Study visit.

Subjects will also be instructed not to apply the IP to cuts, abrasions, eczematous skin and sunburned skin and not to use “waxing” as a depilatory method on skin treated with the IP.

Based on an approximate [REDACTED] of cream should be sufficient to last for the full duration of the study (84 days ± 4 days). Subject kits will each contain [REDACTED] of IP and will be randomized using [REDACTED]. If a subject requires additional IP beyond [REDACTED] in order to complete dosing in the study (i.e., tube lost, all IP used between visits or tube significantly damaged [became punctured]), an additional kit of investigational product may be assigned to the subject using [REDACTED].

[REDACTED]

At each visit, the subject will be provided with a dosing diary in which they will be required to record the date of Day 1, all dosing dates and times and any missed doses. Each diary should be returned at the following visit so that the study staff may check compliance and file in the subject’s source documentation.

10.4.2 Identity of IP

The following products will be used in the study:

- **Test:** Tazarotene Cream 0.1% (Fougera Pharmaceuticals Inc.)
- **Reference:** TAZORAC[®] (tazarotene) Cream, 0.1% (Allergan, Inc.)
- **Placebo:** Placebo (vehicle) Cream (Fougera Pharmaceuticals Inc.)

